3.2 Study Design/Type

This is a pre/post-randomized control study design. Research assistants will collect data at Muriel Clayton Middle School and conduct the statistical analysis. There will be a comparison group that receives a vaping video intervention developed by the National Health Institute, and an experimental group receiving the intervention. Questionnaires will be used to collect data.

Classroom teachers will be given a script that they will use to introduce the study to the students of both groups using the study introduction script. Students will be informed that their responses will be completely anonymized to minimize the risk of social desirability bias. School teachers will help to identify any students who do not meet the inclusion criteria and they will be excluded from the analysis. Each student participating in the study will be given an envelope containing a unique study ID, Personal Information Questionnaire, Video Survey, information sheet describing the study, and a copy of each of the KAS and EHI. KAS and EHI in the envelopes will be labeled "1", signifying pre-intervention. Following the intervention participants will receive another copy of the KAS and EHI labeled "2", signifying post-intervention, which they will place in the envelope after completion. None of the forms will have any identifying information (outside of age, grade, and gender) and the school teachers will not review the data collected. Individuals present in the rooms will include one or more school staff, research assistants going in between rooms if there are more than two rooms, and the student participants. The students will complete the Personal Information Questionnaire, KAS and EHI, prior to watching the intervention video. Following the intervention they will be provided with another copy of the KAS and EHI along with the Video Survey. Once students have completed the questionnaires they will be asked to place everything back in the envelope and hand the envelope to the research assistant.

After completion of the assigned video and associated evaluations, students will be shown the other video. This will be done to ensure that no student is excluded from any of the benefits of either of the treatments.

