3.3 Randomization

Each classroom of grades 7 and 8 at Muriel Clayton Middle School will be divided into group A and B evenly. Research assistants will alternatively place students in groups A Ethics ID: REB23-1437 Date: 1/11/2024 Version: 8 and B based on software (e.g Excel) to produce a randomized sequence of A's and B's. After all students have been assigned they will proceed to their groups' assigned room and receive an envelope. The envelopes will contain the students study ID and will start with the letter A or B corresponding to their assigned group. All students in group A will complete the questionnaires, watch the intervention video, and then complete the same questionnaires immediately after the intervention. All students in group B will complete the questionnaires, experience the control condition (NIH video) and then complete the same questionnaires. The teacher will introduce the study prior to group assignment.

Students not meeting the inclusion criteria will be assigned group C. A set of envelopes with a "C" code will be prepared beforehand and distributed to group C students. These Group C students will follow the same procedure as group A but will be excluded from analysis.

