3.5 Duration

The trial, including pre and post-assessments and intervention delivery, will last approximately 45 to 50 minutes (one school period) of a single school day.

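### Completed pre-video forms stay within students' reach while they answer the identical post-video forms, because the protocol has one hand-in, at the end

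*Protocol*

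**What the plan says.** Protocol Section 3.2 sets out the handling of the forms in this order.

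- At the start, "Each student participating in the study will be given an envelope containing a unique study ID", together with the Personal Information Questionnaire, the Video Survey, an information sheet, and one copy each of the KAS and EHI marked 1.
- Before the video, students fill in the personal questionnaire and copies 1.
- After the video they receive copies 2, "signifying post-intervention, which they will place in the envelope after completion".
- When all questionnaires are finished, "they will be asked to place everything back in the envelope and hand the envelope to the research assistant". This is the only hand-in described.

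Section 3.3 confirms that students "then complete the same questionnaires immediately after the intervention", and Section 3.5 says that the whole session "will last approximately 45 to 50 minutes (one school period) of a single school day". Section 7.1 then builds the analysis variables as each student's pre-to-post difference, on items and totals, and compares these between the arms.

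On the Video Survey, Section 3.2 makes two statements. Students "will be given an envelope containing a unique study ID, Personal Information Questionnaire, Video Survey, information sheet describing the study" at the outset, but later: "Following the intervention they will be provided with another copy of the KAS and EHI along with the Video Survey".

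**The concern.** Students answer the same agreement-scale items twice within one school period. Nothing in the stated procedure puts the first set of answers out of reach before the second set is given. A student who copies has a change of zero whatever the video did. A student who revises copy 1 after the video corrupts the baseline instead. Either act alters the change score itself, and the primary comparison is a comparison of change scores.

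That both arms follow the same procedure does not make it harmless. Equal copying in both arms does not cancel out of a difference in change; it scales that difference down. The comparator is also an anti-vaping video, so a small or null difference is a plausible result, and with this procedure it would be hard to tell a true null from repeated answers. All data come from a single session, so the problem cannot be repaired afterwards.

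**Working it through.** **Step 1: is there a safeguard elsewhere?** Section 3.3 repeats the order questionnaires, video, questionnaires, and adds no collection. Section 3.5 gives only the session length. Section 4.3 refers to envelopes being handed in, again as one event. Section 4.5 has research assistants support compliance with the procedures, but those procedures contain no step for copies 1. Section 3.2 also allows assistants to move between rooms if there are more than two. The instruction to put everything back implies that the contents may still be out at the end.

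**Step 2: the plan's own figure.** Inputs from Sections 7.2 and 7.3: 50 per arm, 80% power, alpha 0.05, detectable differences of 1.52 (KAS) and 3.58 (EHI). The SDs are taken from cited literature and not stated, so these differences cannot be reproduced independently. Assuming a two-sided test and the normal approximation, they can be solved backwards:

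SD = difference / [(1.960 + 0.842) × √(2/50)] = difference / 0.5603

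- KAS: 1.52 / 0.5603 = 2.71
- EHI: 3.58 / 0.5603 = 6.39

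I take these as the SDs of the analysed change.

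**Step 3: equal copying.** Suppose a fraction f of students in each arm copy, so their change is 0. With true mean changes μA and μB, the expected difference becomes (1 − f)μA − (1 − f)μB = (1 − f)(μA − μB). The protocol gives no value for f; 10%, 20% and 30% are assumptions.

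**Step 4: power under three models for the SD.**

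(a) SD unchanged: power = Φ[2.802(1 − f) − 1.960].

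(b) A fraction f copies and the rest respond as planned. The variance in an arm whose non-copiers have mean change μ is (1 − f)SD² + f(1 − f)μ². Example for KAS with f = 0.2 and control mean change 0:
- variances: 0.8 × 7.359 + 0.16 × 2.310 = 6.257 (intervention) and 0.8 × 7.359 = 5.887 (control)
- SE = √(12.144/50) = 0.493
- power = Φ(1.216/0.493 − 1.960) = 69%

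(c) Every student's change shrinks by the factor (1 − f). The SD shrinks by the same factor, so the standardised difference and the power stay as they were.

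| Assumed loss f | KAS difference | EHI difference | (a) SD unchanged | (b) control change 0 | (b) control change equal to the detectable difference | (c) uniform shrinkage |
|---|---|---|---|---|---|---|
| 0% | 1.52 | 3.58 | 80% | 80% | 80% | 80% |
| 10% | 1.37 | 3.22 | 71% | 75% | 73% | 80% |
| 20% | 1.22 | 2.86 | 61% | 69% | 64% | 80% |
| 30% | 1.06 | 2.51 | 50% | 63% | 56% | 80% |

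The power columns are the same for both scales because each starts from 80% at its own detectable difference.

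**Step 5: unequal copying.** Assume on the KAS a control change of −1.52 and an intervention change of −3.04, so the true difference is −1.52.

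- 10% copy in the intervention arm, 30% in control: 0.9 × (−3.04) − 0.7 × (−1.52) = −1.67. The difference is inflated.
- 30% copy in the intervention arm, 10% in control: 0.7 × (−3.04) − 0.9 × (−1.52) = −0.76. The difference is halved.

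**The case against.** **Power need not fall.** Pulling second answers toward first answers also narrows the spread of change scores. With assumed figures, if the pre-post correlation rises from 0.5 to 0.6 while the difference loses 10%, the SD of change falls by the factor √(0.4/0.5) = 0.894. Power is then Φ(2.802 × 0.9/0.894 − 1.960), about 80%. This stands: a reader might take 71%, 61% and 50% as the expected loss, but they hold only if the SD does not move. Under uniform shrinkage the raw difference is still biased even though power is kept.

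**The direction is not fixed.** A reader might infer a sure bias toward no difference. That needs similar copying in both arms, and the protocol says nothing about how often either arm would copy. This stands too.

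**Access to earlier answers is inferred.** The text does not say whether copies 1 go back into the envelope before the video. Staff are in the rooms, and the introduction script and attached supporting documents are not shown. It is fair that actual copying or altering is not shown. But an envelope that stays with the student and is not sealed still leaves the answers within reach, and the protocol's own procedure names no other safeguard.

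**The Video Survey.** A reader might infer that having it early distorts the KAS and EHI comparison. It does not follow: the survey is completed once, has no earlier answers to copy, and asks about the video. Only a wording conflict remains.

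**The remedy has limits.** The pre-post link appears to rest on the shared envelope, since Section 3.2 does not say that each form carries the study ID. Separating copies 1 could break the pairing. Memory of answers given minutes earlier would also persist. Both points stand and limit what the fix can promise.

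**Conclusion.** The point holds as a weakness in data collection that is cheap to remove. As written, the protocol leaves completed pre-video forms open to viewing, copying and alteration while the identical post-video forms are answered, and the primary comparison is built on the difference between the two.

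The documents support no single figure for the effect. With equal copying, the expected difference falls by the copying fraction. With unequal copying, it can be understated or overstated. The power range in the table, from unchanged to the SD-fixed column, rests on assumed loss fractions, a two-sided test and back-solved SDs. It also counts all the shrinkage as avoidable, whereas only the part due to having the forms at hand is.

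The documents do not support saying that students will copy, that power will fall by a known amount, or that the result is necessarily biased toward no difference. The Video Survey conflict is separate and does not bear on the KAS and EHI comparison.

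**What to change.** In Section 3.2:

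1. State that the study ID is printed on every form, so that pre and post answers can be paired without relying on a shared envelope.
2. Before the video starts, have students seal copies 1 in an envelope of their own or hand them to the research assistant.
3. Hand out copies 2 only after the video.
4. Separately, reconcile the two statements on the Video Survey, for example by removing it from the list of starting envelope contents and giving it out after the video.

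The cost is about a minute of class time, ID printing, and a collection step or a second envelope; staff are already assigned to the rooms. The change removes access to earlier answers but not recall of them, so the report should still acknowledge the immediate repeat of the same items as a limitation.

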3.3 Randomization

Each classroom of grades 7 and 8 at Muriel Clayton Middle School will be divided into group A and B evenly. Research assistants will alternatively place students in groups A Ethics ID: REB23-1437 Date: 1/11/2024 Version: 8 and B based on software (e.g Excel) to produce a randomized sequence of A's and B's. After all students have been assigned they will proceed to their groups' assigned room and receive an envelope. The envelopes will contain the students study ID and will start with the letter A or B corresponding to their assigned group. All students in group A will complete the questionnaires, watch the intervention video, and then complete the same questionnaires immediately after the intervention. All students in group B will complete the questionnaires, experience the control condition (NIH video) and then complete the same questionnaires. The teacher will introduce the study prior to group assignment.

Students not meeting the inclusion criteria will be assigned group C. A set of envelopes with a "C" code will be prepared beforehand and distributed to group C students. These Group C students will follow the same procedure as group A but will be excluded from analysis.

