5.2 Method and Timing

The two adapted versions of the validated surveys assess attitudes and perceptions in relation to e-cigarette or "vaping" use. The students will be informed by their teachers prior to survey distribution that e-cigarette terminology and vaping are interchangeable. For both of the surveys, participants rate how much they agree with each statement (on a numbered scale between "*strongly disagree*" and "*strongly agree*") related to vaping/e-cigarette use (*e.g. "e-cigarettes are safer than smoking"*). To determine if there was any difference in attitudes, knowledge, or harm perceptions related to vaping before and after the intervention.

Demographic information collected in the personal information questionnaire will include age, gender, and grade. This information will be used to describe the sample recruited and assessed for variations between different groups. No other identifying personal information will be collected (name, contact information, etc.) and all results will be anonymous.

The *Video Survey* is a questionnaire adapted from a previous study (Hollis et al., 2022) asking students regarding their opinion of the intervention's effect on their vaping knowledge, usefulness to others, and overall knowledge about vaping following the intervention ². This information will be collected to determine how the intervention was perceived by the participants. Students will also be asked if they have vaped to inform on the effect of prior vape use on the perception of the intervention and efficacy and changing attitudes. Short answer questions asking participants what they liked and what they disliked in the intervention will also be included to inform future directions.

6 Assessment of Safety

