7.1 Statistical Methods

Data from questionnaires will be entered into an Excel spreadsheet by research assistants. A double entry will be performed to reduce the frequency of data entry errors. New variables will be created by taking the difference in the individual items and overall scores for KAS and EHI pre and post-intervention for each participant ^{20,21}. In order to ensure that higher scores reflect an increased likelihood of vape abuse, question 10 on the KAS will be reversed scored as a study showed that on this question vape non-users were more likely to score higher than users ²⁰. Descriptive statistics and graphics for participant demographic characteristics and questionnaire responses will be performed prior to primary analysis to detect errors in data, such as missing data and variables being outside of the plausible range. If errors are found they will be addressed. After this, the database will be locked.

Initially, to confirm the validity of creating a total score, we will confirm internal consistency using Crohnbach's alpha. We assume that internal consistency will be adequate and therefore describe an analysis of total scores on the scale in the remainder of this section.

The analysis will begin by describing sample characteristics. Following this, a primary analysis will be undertaken to evaluate the success of the intervention. Imbalances in randomization will be looked at using graphical methods and tables and will be adjusted using linear regressions if the distributional assumptions and the assumption of linearity

are met as assessed with a scatter plot. If the distributional assumptions are not met then quantile regression will be used. T-tests will be performed to assess if the intervention group had a significant change between pre and post-intervention compared to the comparison group on the KAS and EHI. If data is not normally distributed non-parametric tests will be used. The robustness of the primary analysis will be assessed by adjusting for other variables through linear regression models.

An exploratory analysis will be done and will involve using T-tests to determine if the individual item scores for the first 5 questions on the Video Survey are significantly different between the experimental and comparator groups. Mann-Whitney U test will also be used to determine if the two groups responded differently for questions 5 and 6 on the Video Survey.

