7.2 Sample Population(s) for Analysis

Our sample size is limited to the number of grade 7 and 8 students at Muriel Clayton school, approximately 100 students with 50 in the control group and 50 in the experimental group. Based on existing literature on standard deviation (SD) of the surveys we determined the effect size our study can detect with 80% power ^{20, 21}. We determined that our study can detect a difference of 1.52 points on the KAS scale and a 3.58 points on the EHI with 80% power. A study showed that for the KAS cigarette/e-cigarette users and non-users had a mean score of 21.04 and 18.86 respectively when reverse scoring question 10 ²⁰. Considering the difference between the two groups in this study is similar, we have the statistical power to detect it.

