7.3 Significance

The alpha value to be used in the study is 0.05.

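### Pupils are randomised within classroom, but the primary t-test ignores classroom and no classroom code is described; the number of viewing rooms per arm is also left open

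*Protocol*

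**What the plan says.** - **Allocation.** Protocol section 3.3 has each grade 7 and 8 classroom "will be divided into group A and B evenly", using a software-generated sequence. Pupils then go to the room assigned to their group and receive their envelope there. The first questionnaires, the video and the repeat questionnaires all take place in that room.
- **Rooms.** Section 3.2 does not fix their number. It provides for "research assistants going in between rooms if there are more than two rooms".
- **Data held.** Section 5.2: "Demographic information collected in the personal information questionnaire will include age, gender, and grade". Sections 3.3 and 3.4 describe the study ID only by its leading group letter. Section 3.2 says the forms carry nothing identifying beyond age, grade and gender.
- **Analysis.** Section 7.1: "T-tests will be performed to assess if the intervention group had a significant change between pre and post-intervention compared to the comparison group". Regression is used to adjust for imbalances and, as a robustness check, for other variables that are not named.
- **Size.** Section 7.2 assumes "approximately 100 students with 50 in the control group and 50 in the experimental group" and makes no mention of classroom or room.

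**The concern.** Splitting each classroom evenly balances the arms on whatever classmates share. An unadjusted t-test does not use that balance: it leaves the between-classroom variation in the error term. The sample is capped by the size of the school, so precision cannot be bought by recruiting more pupils.

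The choice of model terms can be left to a statistical analysis plan. The collection of a variable cannot. Envelopes are handed out after pupils have left their classroom, and no names are taken. Unless the classroom is coded on the envelope or logged elsewhere, nothing described in the protocol links a completed form to it.

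The room is a different matter. Pupils who watch together share supervision, peer reaction and any disturbance. If all of one arm watches in one room, a disrupted or unusually attentive session would look like an effect of the video.

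**Working it through.** **1. The plan's own figures.** Section 7.2 says the study "can detect a difference of 1.52 points on the KAS scale and a 3.58 points on the EHI with 80% power". With 50 per arm, two-sided alpha 0.05 (section 7.3 gives 0.05 without stating sidedness) and 80% power:

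detectable difference = SD × (1.960 + 0.842) × √(2/50) = 0.560 × SD.

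No SD is printed; the section says only "Based on existing literature on standard deviation (SD) of the surveys". The figures can therefore be back-solved but not reproduced: 1.52/0.560 ≈ 2.71 for the KAS and 3.58/0.560 ≈ 6.39 for the EHI. The formula treats pupils as independent and has no term for classroom or room.

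**2. Classroom.** Let ρ be the share of change-score variance that lies between classrooms. The protocol gives no value, so every ρ here is an assumption. With an even split in each classroom, the classroom component cancels from the difference between arms:

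- true variance of the difference ≈ 2σ²(1 − ρ)/n
- variance assumed by the t-test ≈ 2σ²/n
- gain from adjusting, in pupils = 1/(1 − ρ)

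ρ = 0.05 gives 1/0.95 = 1.05 and ρ = 0.15 gives 1/0.85 = 1.18, so 5% to 18% more pupils. If the stated detectable differences apply to change scores, they would shrink by √(1 − ρ):

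- KAS: from 1.52 to 1.48 (ρ = 0.05) or 1.40 (ρ = 0.15)
- EHI: from 3.58 to 3.49 or 3.30

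The unadjusted standard error is too large by 1/√(1 − ρ): 2.6% at ρ = 0.05, 5.4% at 0.10 and 11.8% at 0.20. The true type I error is 2[1 − Φ(1.96/√(1 − ρ))], which gives 0.044, 0.039 and 0.028. Simulation of the t-test (20,000 runs, 48 per arm, four classrooms assumed) gave 0.047, 0.042 and 0.033. The error is on the conservative side throughout.

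**3. Room.** Let m be pupils per room and ICC the room correlation in change scores, again assumed. Design effect DE = 1 + (m − 1) × ICC; type I error of the unadjusted test ≈ 2[1 − Φ(1.96/√DE)].

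| Rooms per arm | m | ICC 0.01 | ICC 0.02 | ICC 0.05 | Between-room df |
|---|---|---|---|---|---|
| 1 | 50 | DE 1.49, 11% | DE 1.98, 16% | DE 3.45, 29% | 0 |
| 2 | 25 | DE 1.24, 8% | DE 1.48, 11% | DE 2.20, 19% | 2 |

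Simulation agrees: 0.111, 0.162 and 0.297 with one room per arm; 0.077, 0.110 and 0.182 with two. At ICC = 0 the error stays at 5%.

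The last column matters most. Between-room degrees of freedom are 2 × (rooms per arm − 1). With one room per arm there are none, so a room effect cannot be estimated and no adjustment is possible.

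**The case against.** **The protocol does not say that classroom goes unrecorded.** This stands. Only the first character of the study ID is described, and the regression covariates are not named. The finding is that the described data carry no classroom code, not that one is ruled out.

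**Change scores already remove stable differences.** Largely right. A classroom that starts high is high on both occasions, and the baseline is completed in the same room as the repeat, so stable classroom and room levels cancel. Only variation in change matters, and it may be small. Grade, which is collected, may also carry part of any classroom difference.

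**Three stronger readings are tempting, and the documents support none of them.**
- *The standard errors make the test invalid.* The two influences act in opposite directions. Ignoring the blocks makes the standard error too large. Only sharing a room can make it too small, by an unknown amount.
- *There is one room per arm, so room and video are fully confounded.* Section 3.3 reads most naturally that way, but section 3.2 allows more than two rooms. Full confounding holds only if one room per arm is what happens.
- *The trial's true error rate is 8% to 29%.* Those figures illustrate assumed room ICCs of 0.01 to 0.05. They are not properties of this trial.

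**Recording the room would not help in the worst case.** Correct. With one room per arm, the group letter already identifies the room. With two to four rooms in all, clustering on room is unreliable.

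**Conclusion.** The point holds in a limited form. Classroom is a randomisation block that the stated primary analysis ignores and that the described data would not hold. The consequence is lost precision, worth about 5% to 18% of the sample if classroom explains 5% to 15% of change-score variance, and close to nothing if it explains close to none. It does not threaten validity. It is worth acting on because the remedy is cheap before the study day and may be impossible afterwards.

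The room part is a design limitation. The protocol leaves the number of rooms open. If it is one per arm, events in that room between the first and second questionnaires cannot be told apart from the effect of the video. The size of any such effect cannot be derived from the protocol.

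**What to change.** 1. **Classroom.** Add an arbitrary classroom code to the study ID and fit classroom as a fixed effect in the primary model, whether that models change or the post-test score adjusted for baseline. Because envelopes are now given out in the viewing room, they would have to be sorted by classroom or handed out before pupils move. The cost is one degree of freedom per classroom beyond the first, and smaller cells when the code is combined with age, gender and grade. That loss of anonymity should be weighed against the assurance to pupils in section 3.2. An arbitrary code reduces the problem but does not remove it.
2. **Rooms.** State the number of rooms per arm in section 3.3 and reconcile it with section 3.2.
   - If there is one per arm, say that the comparison is of video and viewing session together, and limit the conclusion to that.
   - If there are several rooms or sessions per arm, record the room on the envelope. Where sessions permit, alternate rooms and supervising staff between arms. The single school period in section 3.5 may not leave space for separate sessions, in which case the stated limitation is all that remains.

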1.6 Participant Population

Grade 7 and 8 students from Muriel Clayton Middle School in Airdrie, Alberta, Canada. Students must be able to understand the language of the video and the evaluation questionnaires, any students unable to understand the language due to either language barriers or developmental delays will be identified by the teachers and excluded from the analysis—although they will be provided the option to be present for the room viewings and even fill out the questionnaires to avoid singling them out.

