4.1 Inclusion Criteria

- Attend Muriel Clayton Middle School
- Be in grade 7 or 8
- Be enrolled in the standard Alberta grade 7 or 8 curriculum
- Provides implied consent
- Parent or guardian provides written consent
- Able to understand the language of the video

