4.2 Exclusion Criteria

- Younger than 11 years old
- Older than 16 years old
- Does not provide implied consent
- The parent or guardian does not provide written consent
- Unable to understand the language of the video or questionnaire due to language barriers of developmental delay

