7.6 Deviation Reporting

This report will be archived on PRISM at University of Calgary.

8 Direct Access to Source Data/Documentation

There are no permits, contracts, or regulatory audits.

9 Quality Control and Quality Assurance

Quality control and quality assurance will be done in adherence to GCP

10 Research Ethics Considerations

This study will be conducted according to the Tri-Council Policy Statement 2022 and international standards of Good Clinical Practice for all studies. University of Calgary research policies and procedures will also be followed.

This protocol and any amendments will be submitted to the University of Calgary CHREB for review and approval prior to conduct. The decision of the CHREB concerning the conduct of the study will be provided electronically to the investigator. An application will also be submitted to the Rocky View Division Research Committee in order to obtain permission to conduct research at Murial Clayton Middle School.

All parents/guardians of the participants for this study will be provided a consent form describing this study and providing sufficient information for parents of participants to make informed decisions about their children's participation in this study. The consent form must be signed by the participant's parent/guardian or legally acceptable surrogate/third-party. This consent form will be submitted with the protocol for review and approval by the CHREB. The implied consent of a participant will be obtained before that participant is submitted to any study procedure.

11 Data Handling and Record Keeping

The Excel file and analysis files will be stored in an encrypted drive in a password-protected computer that will be stored in a secure location. The dataset stores will have no names in them.

12 Finance and Insurance

No personnel costs, and minor costs (e.g. printing) will be covered by the Cuthbertson & Fischer Chair in Pediatric Mental Health.

13 University of Calgary Legal Approval

Legal approvals are not required for this study

14 Supplements

Supporting Documents (Questionnaires and Surveys) are attached

15 References

[1] Diez, S. L., Cristello, J. V., Dillon, F. R., De La Rosa, M., & Trucco, E. M. (2019). Validation of the electronic cigarette attitudes survey (ECAS) for youth. Addictive behaviors, 91, 216–221. https://doi.org/10.1016/j.addbeh.2018.11.022

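### As worded, the group C rule takes in pupils without consent and puts them through study procedures, against section 10 and beyond section 1.6; where group C sits is also left open

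*Protocol*

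**What the plan says.** **The rule.** Protocol section 3.3 (Randomization) states: "Students not meeting the inclusion criteria will be assigned group C". These pupils receive C-coded envelopes prepared in advance, and "These Group C students will follow the same procedure as group A but will be excluded from analysis". Group A's procedure is questionnaires, the locally produced video, then the same questionnaires again. Section 3.4 refers to holders of C-coded study IDs as participants and excludes them only from the analysis.

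**Who fails an inclusion criterion.** Section 4.1 lists "Provides implied consent" and "Parent or guardian provides written consent" alongside school, grade, curriculum and language. Section 4.2 repeats the consent criteria in the negative, for example "The parent or guardian does not provide written consent".

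**The consent section.** Section 10 (Research Ethics Considerations) says of the parental form: "The consent form must be signed by the participant's parent/guardian or legally acceptable surrogate/third-party". Of the pupil it says: "The implied consent of a participant will be obtained before that participant is submitted to any study procedure".

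**The narrower arrangement.** Section 1.6 concerns pupils whom teachers identify as unable to follow the language, because of a language barrier or developmental delay. They are "excluded from the analysis—although they will be provided the option to be present for the room viewings" and may also complete the questionnaires, so that they do not stand out.

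**Rooms.** Section 3.3 sends pupils to the room of their group and names none for group C. Section 3.2 allows for more than two rooms.

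**The concern.** Research assistants will work on the day from section 3.3. If they apply it as written, a pupil whose parent has not signed is given a coded envelope, fills in the study forms twice and watches the video. Leaving the C envelopes out of the analysis does not undo that collection. Two other sections raise the stakes. Section 5.2 says pupils will be asked whether they have vaped. Section 4.3 allows no withdrawal once the envelope has been handed in, so the protocol gives no way to take back forms collected in error.

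The second matter concerns the comparison itself. Group C is tied to group A's procedure only. If its pupils also share group A's room, the intervention is always viewed in company that includes ineligible pupils and the comparator never is. Any influence of that setting on group A's answers would stay in the group A data after the C envelopes are removed.

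**Working it through.** No arithmetic is needed for the main point; it follows from reading the sections together.

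1. **Entry to group C.** Section 3.3 uses failure of the inclusion criteria as the test, without listing which criteria and without exceptions.
2. **Consent is such a criterion.** Section 4.1 includes both written parental consent and implied consent. A pupil lacking either fails the test in step 1 and belongs to group C.
3. **What follows for that pupil.** Under section 3.3, group A's full procedure. The only thing withheld is inclusion in the analysis.
4. **Does section 10 apply to group C?** Its requirements are framed in terms of participants. Section 3.4 uses that word for group C and gives its members study IDs, so the protocol's own terms bring them under section 10.
5. **The conflict.** For a pupil without a signed parental form, sections 3.3 and 10 cannot both be followed.

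The two kinds of consent differ in strength. The timing in section 10, ahead of study procedures, is attached to the pupil's implied consent; the parental sentence requires a signature without stating when. On the other hand, a pupil's implied consent might be read from the act of completing the forms, and section 4.3 gives a pupil who does not wish to continue a way out. Nothing comparable can stand in for a parent's signature, so the parental part is the firmer one.

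**Section 3.3 against section 1.6:**

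| | Section 1.6 | Section 3.3 |
|---|---|---|
| Who | Pupils unable to follow the language | Any pupil failing any inclusion criterion |
| Attendance | Optional | Stated as what they will do |
| Questionnaires | Optional | Part of group A's procedure |
| Video | Not specified | Group A's |

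**Seating.** Let c be the number of pupils in group C, all seated with group A. Section 7.2 gives about 100 pupils, 50 per group.

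- If c comes out of the 100: A viewings hold (100 − c)/2 + c = (100 + c)/2 pupils and B viewings (100 − c)/2. The difference is c.
- If c is additional to the 100: 50 + c against 50. The difference is again c.

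The protocol gives neither c nor a consent rate. Section 3.3 also divides each classroom separately, so these totals need not be the headcount of any one sitting. The calculation shows the direction of the imbalance under shared seating, and no more.

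**The case against.** The strongest reply is that section 3.3 is loosely worded and the rest of the protocol shows what is meant. Section 4.2 excludes pupils without consent, section 10 makes the signature mandatory, and section 1.6 describes a group C-like arrangement for language and developmental reasons alone. On that reading consent is settled first and group C is simply the section 1.6 population. Consent pages are also absent from the public copy and may say how pupils without consent are handled.

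This is a plausible account of intent, and it rules out saying that the trial would in fact collect data from pupils without consent. It does not remove the contradiction: exclusion under section 4.2 is compatible with being sent to group C, section 3.3 is the operative instruction, and no section makes an exception to it.

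On the rooms, a reader might infer that the rule makes the intervention room differ from the comparison room and so biases the result. The protocol does not support that as a statement of fact. Following the same procedure is not the same as sitting in the same room, and a third room is possible. Sections 3.2 and 4.5 place staff and research assistants in the rooms without distinguishing the arms, so unequal attention is conjecture. What stands is a conditional point: the aim in section 1.6 of not singling pupils out suggests shared seating, and a separate room for group C would work against that aim.

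**Conclusion.** The consent contradiction holds on the text alone and should be corrected before any pupil is assigned. Read literally, section 3.3 covers pupils without parental or own consent, contrary to section 10 and wider than section 1.6. It is a conflict in wording that would lead to a serious error if followed; it is not evidence of what the investigators intend.

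The seating point is secondary and depends on group C sitting with group A. If it does, only the intervention viewings contain ineligible pupils. Any effect on the Knowledge and Attitudes or Harm Perception scores would be indirect, through the setting. A reader might put a figure on it by assuming a consent rate and deriving room sizes, but the documents contain nothing to support such a rate. Neither the size of group C nor the size or direction of any bias can be derived.

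**What to change.** **Main change.** Reconcile section 3.3 with sections 1.6 and 10:

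- Restrict group C to pupils who have both consents and are excluded for language or developmental reasons, with attendance and form-filling optional as in section 1.6.
- State that pupils without consent receive no study envelope, complete no study forms and are not assigned to a study group.

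**Secondary change.** State where group C sits. Divide its pupils at random between the A and B rooms, with envelope codes CA and CB, both excluded from analysis. Section 3.2 already has the other video shown to students after their evaluations, so a group C pupil placed with group B need miss neither video.

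**Cost.** A few sentences of protocol text, a second envelope code, and an ordinary class activity for one period for pupils without consent. That last item makes those pupils more visible to classmates, which the school would need to plan for. The analysis plan and the sample-size statement need no change.
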